## **2.5. Exploratory objectives to be assessed only if and when a correlate of protection has been established for both vaccine candidates**

Separately for adults and children:

- To compare the three vaccine strategies with one another for the correlate of protection response at 28 days and 12 months after randomization. For the comparison at 28 days, the two rVSVΔG-ZEBOV-GP groups will be combined.
- To compare the group randomly assigned to the Ad26.ZEBOV prime with the two groups (pooled) assigned the rVSVΔG-ZEBOV-GP prime vaccine for the correlate of protection response 14 days after randomization (immediacy of response).
- To compare the three vaccine strategies with one another for the correlate of protection response 3 months after randomization.

For pooled analysis of children and adults:

- To compare the three vaccine strategies with one another for the correlate of protection response 28 days and 12 months after randomization (prime vaccination) (durability of response). For the comparison at 28 days the two rVSVΔG-ZEBOV-GP groups will be combined.
- To compare the Ad26.ZEBOV prime vaccination with the rVSVΔG-ZEBOV-GP prime vaccination (2 rVSVΔG-ZEBOV-GP groups combined) for the correlate of protection response 14 days after randomization (immediacy of response).
- To compare the group randomly assigned to the Ad26.ZEBOV prime with the two groups (pooled) assigned the rVSVΔG-ZEBOV-GP prime vaccine for the correlate of protection response 28 days after randomization.
- To compare the three vaccine strategies with one another for the correlate of protection response 3 months after randomization.
- To compare the three vaccine strategies with one another for percent of participants who experience SAEs through 12 months after randomization.
- To compare the three vaccine strategies with one another for the correlate of protection response and safety outcomes by age.

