**Background and Rationale:**

Preliminary data from an open-label, cluster randomized ring vaccination trial conducted in Guinea indicate that the Merck/New Link rVSVΔG-ZEBOV-GP vaccine prevented Ebola virus (EBOV) disease (EVD) events occurring at least 10 days after randomization among close contacts immediately vaccinated as

compared to those to be potentially vaccinated 21 days later. In that trial conducted in adults, most EVD events occurred shortly following vaccination; no EVD events occurred more than 6 days after vaccination. The durability of the effect of the vaccine was not assessed.

Two other vaccines, the GlaxoSmithKline (GSK) ChAd3-EBO Z (replication deficient Chimpanzee adenovirus type 3-derived vector encoding the Ebola virus Zaire [EBO Z] GP) vaccine and the Johnson & Johnson (J&J) prime boost vaccine, rHAd26/MVA, have completed phase 1 testing. In addition, safety and immunogenicity after 12 months of the rVSVΔG-ZEBOV-GP and ChAd3-EBO Z vaccine have been evaluated in a phase 2, placebo-controlled trial of adults in Liberia (Partnership for Research on Ebola Virus in Liberia [PREVAIL] I).

By the end of 2015 in West Africa, the incidence of EVD had dramatically decreased. However, multiple questions regarding the safety and effectiveness of EVD vaccines remain unanswered, including the durability and the immediacy of immune responses generated by different vaccine strategies with and without a booster, and the safety of the different vaccines, particularly in children.

In order to answer these questions, a randomized trial that includes adults and children will be carried out. The trial will compare three vaccine strategies with placebo for immunogenicity and safety. The comparisons will be carried out separately for adults and children and for adults and children combined. The three vaccine strategies are: 1) Ad26.ZEBOV (prime) (0.5 mL) followed by an MVA-BN-Filo boost (0.5 mL) at 56 days; 2) rVSVΔG-ZEBOV-GP (prime) (1 mL) with a placebo (1 mL) boost at 56 days; and 3) rVSVΔG-ZEBOV-GP (prime) (1 mL) with a rVSVΔG-ZEBOV-GP boost (1 mL) at 56 days. There will be two placebo groups, one with a syringe fill volume of 0.5 mL to match the fill volumes of the Ad26.ZEBOV and MVA-BN-Filo vaccines and the other with a fill volume of 1 mL to match the fill volume for the rVSVΔG-ZEBOV-GP vaccine. The two placebo groups will be combined for data analyses.

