#### **1.2. Rationale**

As described above, in an open-label, cluster randomized ring vaccination trial of adults conducted in Guinea, the Merck rVSVΔG-ZEBOV-GP vaccine prevented EVD events diagnosed 10 days or more after randomization among close contacts immediately vaccinated as compared to those eligible to be vaccinated 21 days later. In that trial many EVD events occurred within 10 days of randomization. Immunogenicity testing was not performed.

The J&J prime boost vaccine regimen, rHAd26/MVA, has completed phase 1 testing in adults and is currently being evaluated in phase 2 and 3 clinical trials.

Multiple questions regarding the safety and effectiveness of EVD vaccines remain unanswered, including the immediacy of immune responses generated by the Ad26.ZEBOV and rVSVΔG-ZEBOV-GP vaccines, the durability of the immune response following a booster at 56 days (MVA-BN-Filo following Ad26.ZEBOV

prime and repeat rVSVΔG-ZEBOV-GP following rVSVΔG-ZEBOV-GP prime), and the safety of the different vaccine strategies.

During the EVD epidemic in West Africa a considerable proportion of patients were children and the mortality rate in those aged < 5 years was very high: 89.5% (CI 95%: 75.9, 95.8). No published safety and immunogenicity data are available for children, but at least four clinical trials enrolling children are ongoing.

There is a need for additional effective vaccines for adults and children in the event that EVD incidence increases or the current outbreak is prolonged by new chains of sexual transmission. There are too few cases of EVD to conduct a trial with EVD as the outcome. Thus, the proposed trial will evaluate the safety and immunogenicity of three vaccine strategies in adults and in children.

The trial will include a placebo group and will be powered to compare each vaccine strategy with placebo separately for adults and children for the antibody response at 12 months. Consideration was given to using an active vaccine as the control in children but in order to provide the best safety data of each vaccine strategy, a “true” placebo (saline) is used as the comparator.

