### **2.1. Study design**

After obtaining informed consent, participants will be randomized to the following 5 groups in a 2:1:2:1:1 allocation 1) Ad26.ZEBOV (prime) (0.5 mL) followed by an MVA-BN-Filo boost (0.5 mL) at 56 days; 2) placebo (prime and boost at 56 days) (0.5 mL); 3) rVSVΔG-ZEBOV-GP (prime) (1 mL) followed by placebo boost (1 mL) at 56 days; 4) rVSVΔG-ZEBOV-GP (prime) (1 mL) followed by rVSVΔG-ZEBOV-GP boost (1 mL) at 56 days; and 5) placebo (prime and boost at 56 days) (1 mL) (Figure 1). At 56 days, participants assigned to the rVSVΔG-ZEBOV-GP vaccine without a boost and the two placebo groups will receive a placebo vaccination. Those initially given the Ad26.ZEBOV vaccine will receive the MVA-BN-Filo vaccine at 56 days. Those assigned to the boosted rVSVΔG-ZEBOV-GP arm will receive a booster vaccination with the rVSVΔG-ZEBOV-GP vaccine at 56 days.

In each of the groups receiving the rVSVΔG-ZEBOV-GP vaccine (prime or boost), the undiluted dose of the rVSVΔG-ZEBOV-GP vaccine will be used.

The trial will be conducted at sites in Guinea, Liberia, Mali, and Sierra Leone.

In the event of a new Ebola epidemic, the study design, including the use of placebos, will be re-considered.

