If a correlate of protection is identified, the vaccine strategies will be compared with one another at multiple time points. For the contrast with the smallest sample size (200 adults or children assigned rVSVΔG-ZEBOV-GP with a boost versus 400 vaccinated with rHAd26/MVA or rVSVΔG-ZEBOV-GP without a boost), power is 0.83 to detect an absolute difference of 15% in the antibody response (50% versus 35%) at the 0.0167 (2-sided) level of significance, assuming 10% of participants are excluded due to a positive antibody level at entry or for missing data. If the percent with a positive antibody response at 12 months is 75%, power is 0.87 to detect a 15% lower antibody response for this planned contrast.

For SAEs, we estimate that 5% of participants in the placebo group will experience an SAE by 12 months. This estimate is based on data from PREVAIL I where after 12 months of follow-up 11.8% of participants assigned to placebo developed an SAE. In PREVAIL I most of the SAEs were due to malaria events which did not require hospitalization. Thus, with the exclusion of laboratory confirmed malaria events that did not require hospitalization, the 12 month percent with SAEs in this study is expected to be lower. Among adults and children, considered separately, with type 1 error = 0.0167 (2-sided), power is 0.88 to detect an increase of 7% (to 12%) for the rHAd26/MVA and for the rVSVΔG-ZEBOV-GP without a boost strategies compared to placebo assuming 400 per group. For the rVSVΔG-ZEBOV-GP with a boost (N=200) versus placebo (N=400) comparison for adults and children, power is 0.86 to detect an increase of 9% (to 14%).

Sample size is also sufficient for comparing the vaccine strategies with the pooled placebo group for the antibody response at day 14 (an important secondary objective that address the immediacy of the immune response). For example, if the antibody response at 14 days is 25% in a vaccine group and 7% in the placebo group, fewer than 250 participants total are needed.

A sample size re-estimation will be performed before enrolment has been completed to ensure there is adequate power for both adults and children to address the primary objectives.

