#### 2.1.4 Immunogenicity outcomes

The primary endpoint specified in the protocol by the PREVAC group is the percentage of antibody responders at 12 months. An antibody responder at 12 months is defined as a participant who experiences a 4-fold increase in antibody level from baseline (i.e., a .6 increase on the  $\log_{10}$  scale) and for whom the antibody level at 12 months is  $\geq 200$  EU/mL. With this definition, participants with a missing baseline or 12 month result will be excluded. Also, with this definition, there will be no exclusion of participants with elevated antibody levels at entry.

Each of the 3 vaccine strategies will be compared with the pooled placebo group at the 0.0167 (2-sided) level of significance. Analyses will be carried out for adults and children separately and combined.

This same definition will be used for defining responders at 7, 14, 28, 56, and 63 days and at 3 and 6 months. For the comparisons with the pooled placebo group at 7, 14, 28, and 56 days, the two rVSV strategies will be combined. The two pair-wise comparisons at these time-points, each vaccine strategy versus pooled placebo, will be carried out at the 0.025 (2-sided) level of significance.

As a sensitivity analysis, for the above analyses based on responders, participants with an antibody level  $\geq 200$  EU/mL at baseline will be excluded.

The following additional summaries of antibody levels will be carried out, separately for children and adults:

- Geometric mean titers at 7, 14, 28, 56, and 63 days, and 3, 6 and 12 months separately for adults and children. Comparison groups will be defined as above for version 4.0 participants at day 63 and months 3 and 6. For 7, 14, 28, and 56 days, the rVSV vaccine groups with and without the boost will be combined. Analysis of covariance with stratification by site and with baseline  $\log_{10}$  antibody level as a covariate will be used to compare each vaccine group versus the pooled placebo for  $\log_{10}$  antibody levels at each follow-up visit (geometric mean ratios will be cited).
- Fold increase from baseline to 14 and 28 days, and 6 and 12 months (<2, 2 to < 4, 4 to < 8, 8 to <16,  $\geq 16$ ).
- Box plots of antibody levels at 14 and 28 days, and 6 and 12 months. For days 14 and 28 the rVSV vaccine groups with and without the boost will be combined.

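### The added effect of the second rVSV dose has no prespecified direct estimate or confidence interval unless a correlate of protection is established for both vaccine candidates

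*Protocol*

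**What the plan says.** Protocol 2.1 sets the design: "participants will be randomized to the following 5 groups in a 2:1:2:1:1 allocation". The unboosted and boosted rVSV arms are therefore in a 2:1 ratio, about 400 v 200 in adults and again in children.

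The booster is among the questions the protocol calls open. The synopsis (Background and Rationale) says that several remain, "including the durability and the immediacy of immune responses generated by different vaccine strategies with and without a booster". Protocol 1.2 names "the durability of the immune response following a booster at 56 days", for both MVA-BN-Filo and repeat rVSV.

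The planned comparisons run against placebo. Protocol 7.1 compares each of the three strategies with pooled placebo for outcomes after Day 56. SAP 2.1.4 does the same for the primary endpoint: "Each of the 3 vaccine strategies will be compared with the pooled placebo group at the 0.0167 (2-sided) level of significance". SAP 2.1.5 follows the same pattern for safety, with an optional comparison against matching placebo.

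Strategies are compared with one another only in Protocol 2.5, under the heading "Exploratory objectives to be assessed only if and when a correlate of protection has been established for both vaccine candidates". That list includes SAEs through 12 months. The SAP contains no comparison between strategies.

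Protocol 2.7 nevertheless sizes this contrast, "200 adults or children assigned rVSVΔG-ZEBOV-GP with a boost versus 400 vaccinated with rHAd26/MVA or rVSVΔG-ZEBOV-GP without a boost", and states two powers for it: "power is 0.83 to detect an absolute difference of 15% in the antibody response (50% versus 35%) at the 0.0167 (2-sided) level of significance", and "If the percent with a positive antibody response at 12 months is 75%, power is 0.87 to detect a 15% lower antibody response".

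**The concern.** A reader of the 12-month report will want to know whether a second rVSV dose changes the antibody level at one year, and at what cost in reactogenicity. The trial randomised people concurrently to answer exactly that contrast: same product, same antigen, same assay. The plan gives each arm's result against saline and leaves the difference between the arms without an estimate, an interval or an alpha.

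Two significant results against placebo say nothing about that difference. If the contrast is added only after unblinding it becomes post hoc. For safety, placebo is also not the comparator that isolates the second dose. The arm given the same prime and a placebo booster is.

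**Working it through.** **Inputs.** Arm sizes 200 v 400 per age group, 10% loss (so 180 v 360) and alpha 0.0167 two-sided: Protocol 2.7. Responders at 12 months 79.5% on rVSV and 6.8% on placebo: the earlier Liberian trial, as cited in Protocol 2.7. Attendance at 12 months 95.3% of adults and 96.5% of children: SAP 2.1.2, which supports about 190 v 380. The SD of log10 antibody is not given, so 0.4 to 0.7 is assumed.

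**Step 1: the plan's own powers.** Power = Φ[(|p1 − p2| − z × SE0) / SE1]. SE0 uses the pooled proportion, SE1 the separate proportions, and z = 2.393 for alpha 0.0167.

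- 50% v 35% (n = 180, 360): pooled p = 0.40; SE0 = √(0.24 × (1/180 + 1/360)) = 0.0447; SE1 = 0.0450; (0.15 − 0.1070)/0.0450 = 0.956; power 0.830. With the rates swapped between arms, 0.825. Stated: 0.83.
- 75% v 60%: pooled p = 0.65; SE0 = 0.0435; SE1 = 0.0413; (0.15 − 0.1042)/0.0413 = 1.108; power 0.866. Swapped, 0.877. Stated: 0.87.

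Both reproduce. The contrast was sized, then made conditional.

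**Step 2: what the placebo tests can show.** For 79.5% v 6.8% with 180 v 360: SE0 = 0.0422, SE1 = 0.0329, (0.727 − 0.1011)/0.0329 = 19, so power is 1.00. The unboosted arm (360 v 360) gives 1.00 too. Both tests should succeed whether or not the booster adds anything.

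**Step 3: the direct contrast on responders.** Unboosted rate taken as 79.5%.

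| Population | n | Boosted rate | Power, alpha 0.0167 | Power, alpha 0.05 |
|---|---|---|---|---|
| One age group | 180 v 360 | 89.5% | 0.71 | 0.85 |
| One age group | 180 v 360 | 84.5% | 0.15 | 0.28 |
| Combined | 360 v 720 | 89.5% | 0.97 | 0.99 |
| Combined | 360 v 720 | 84.5% | 0.33 | 0.51 |

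The 95% CI half-width is 1.96 × √(0.795 × 0.205 × (1/180 + 1/360)) = 0.072, about 7 points per age group. It is about 5 points combined.

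**Step 4: the direct contrast on antibody level.** Detectable log10 difference at 90% power = (z + 1.2816) × SD × √(1/n1 + 1/n2); geometric mean ratio = 10 to that power.

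| Assumed log10 SD | 190 v 380, alpha 0.05 | 180 v 360, alpha 0.0167 |
|---|---|---|
| 0.4 | 1.30 | 1.36 |
| 0.5 | 1.39 | 1.47 |
| 0.6 | 1.49 | 1.59 |
| 0.7 | 1.59 | 1.72 |

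**The case against.** The restriction is deliberate, disclosed and repeated through the protocol. No correlate is known, and Protocol 1.1.3 reports macaques protected by this vaccine despite low neutralising antibody. A higher titre after a booster need not mean better protection. Protocol 7.2 also provides for updating the SAP if a correlate is found.

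This limits what the contrast would mean clinically, and that part stands. It does not justify leaving the estimate out. The primary objective itself compares antibody levels without a correlate, and SAEs need none. The worry about comparing different products does not arise within one product and one assay.

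The second objection is that much is already reported. After Day 56 the two rVSV arms appear separately, with geometric mean titres, fold rises, box plots (at 6 and 12 months) and adjusted ratios against the same placebo group. A reader could divide one ratio by the other. That is true, and it narrows the gap to a prespecified estimate with its interval. The interval cannot be read off the two published ones, because both share the placebo group.

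A reader might go further and infer that the trial leaves its own booster question unanswered. The documents do not support that. The open questions in the synopsis and Protocol 1.2 can fairly be read as durability under each regimen, and the results of each arm against placebo do describe that. Nor does any section say that the 400-participant boost arm exists to measure the booster's added effect. Protocol 2.7 explains the surplus sample size by correlate-based comparisons, subgroups and raised baseline antibodies.

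**Conclusion.** The point holds as a cheap improvement to the analysis plan. It is not a flaw in the primary analysis. No direct boosted v unboosted rVSV estimate is prespecified for antibody or safety outside the correlate condition, and the placebo comparisons cannot supply one.

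It would be tempting to add that the trial is already large enough. That holds only for larger effects. A 10-point responder gain is detectable with moderate to good power per age group and high power combined; a 5-point gain would probably be missed. On antibody level, ratios of about 1.3 to 1.7 are detectable at 90% power, depending on the SD and alpha.

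These figures rest on two assumptions. The 79.5% comes from an earlier trial whose responder definition differs from the SAP's (4-fold rise and at least 200 EU/mL). The SD range is assumed throughout.

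**What to change.** Before unblinding, add to SAP 2.1.4 a contrast of rVSV + rVSV v rVSV + placebo booster by randomised group, labelled secondary or exploratory:

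- Month 12 as the main time point, Month 3 as supporting; adults, children and combined.
- The ANCOVA already planned there (log10 antibody, baseline log10 antibody, site), giving the geometric mean ratio with 95% CI; and the site-stratified responder difference with 95% CI.
- The same contrast in SAP 2.1.5 for post-boost reactogenicity and SAEs, without the correlate condition.
- A sentence saying that the emphasis is on estimation, and that an interval including no difference does not show that the booster has no effect.

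Leave comparisons between the two products conditional on a correlate.

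The cost is a paragraph and a table, with no new data and no primary alpha. It is more than one extra number: 2 visits × 3 populations × 2 measures = 12 antibody estimates, plus safety, without multiplicity control. Responder precision is limited within each age group. If the data have already been unblinded, report the contrast as post hoc.

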## **2.6. Endpoints**

The primary immunogenicity endpoint is the GP-EBOV antibody response 12 months after randomization. This endpoint will be used to compare the immunogenicity of the three vaccine strategies with placebo. The primary analysis for adults and children will be performed for participants who do not have elevated antibody levels at baseline.

GP-EBOV antibody response at Day 28 after randomization. For rVSVΔG-ZEBOV-GP arms only, Day 28 post first vaccination will be used for regulatory purposes for comparison to other studies and for bridging children to adults. The primary analysis for adults and children will be performed for participants who do not have elevated antibody levels at baseline.

GP-EBOV antibody response at Month 3 after randomization (approximately 28 days after the booster vaccination). For the rHAd26/MVA vaccine arm only, Month 3 will be used for regulatory purposes. The primary analysis for adults and children will be performed for participants who do not have elevated antibody levels at baseline.

Antibodies to the Ebola virus GP will be measured with the Filovirus Animal Nonclinical Group (FANG) ELISA assay if available. Other assays may also be used. If a correlate of protection is identified, stored sera will be used to measure the correlate and carry out comparisons of the three vaccine strategies with placebo and with one another. The precise definition of antibody responders will be defined by the trial steering committee prior to their unblinding of the study results. The primary analysis will exclude participants with elevated antibody levels at entry.

There are a number of secondary endpoints. Antibody levels will be determined at multiple time points to assess the immediacy and long-term durability of the response. SAEs through 12 months will be collected. AEs of lesser severity, including injection site reactions and targeted symptoms, will be collected following the initial vaccination and following the booster. In addition, substudies will examine T cell and memory B cell changes and viral shedding.

## **2.7. Sample size**

Sample size was established for the 5-arm study to provide power to compare safety and immunogenicity separately for adults (N=1,400) and children (N=1,400) (see [Figure 1](#)). Under Versions 2.0 and 3.0 of the PREVAC protocol 1,700 to 1,800 participants (537 in Version 2.0 and an estimated 1,200 in Version 3.0) are likely to be randomized. Thus, the total number randomized cumulatively in Version 2.0, 3.0 and 4.0 could be over 4,500 participants. A statistical analysis plan describes how data from Version 2.0 and Version 3.0 will be combined with data from Version 4.0 for selected objectives.

Sample size for adults for Version 4.0 has been reduced from what was originally planned (from 3,500 to 1,400). In part, this is because of the delays, and resulting costs, incurred before Version 4.0 could be implemented; in part, this is because a very conservative estimate of sample size was specified for adults in earlier versions of the PREVAC protocol; and in part, this is because of the plan to use data collected in Version 2.0 and 3.0 with data collected in Version 4.0 to address some objectives. Even with this reduction in sample size for adults, power for comparing the major efficacy and safety outcomes for adults and children separately is excellent.

Sample size is greater than what is required to address the primary objectives because if a correlate of protection is identified, the vaccine strategies will be compared with one another for that correlate using an intention to treat analysis. Expected differences between vaccine groups may be smaller than comparisons with placebo and the correlate may have greater variability than the assay which will be used to measure antibody levels to address the primary, secondary and exploratory objectives. The larger sample size will also permit the exploration of subgroups and preserve power in the event there are more participants with elevated antibodies at baseline than anticipated.

For the planned antibody comparisons of each vaccine strategy versus placebo at 12 months, the planned sample is based on data from PREVAIL I. In PREVAIL I antibody levels measured at baseline, one week and at one month are briefly summarized below.

- 4.0% of participants had elevated antibodies to the EBOV at baseline. An elevated baseline antibody level in PREVAIL I was defined using the distribution of antibody levels measured from sera collected in 2004 and 2001 from 92 adults in Mali, a region where there had been no reports of ZEBOV transmission or disease during this time period. Baseline antibody levels were considered elevated in PREVAIL I if they were greater than 3 standard deviations (SD) above the mean (607 enzyme-linked immunosorbent assay units/mL based on the FANG ELISA assay).
- Among participants without elevated antibodies at baseline (96%), the percent with an antibody response at week 1 was 2.5% for those given the rVSVΔG-ZEBOV-GP vaccine and 1.5% for those given placebo (p=0.36). By month 1 antibody levels had increased substantially and 83.7% of participants given the rVSVΔG-ZEBOV-GP vaccine had an antibody response as compared to 2.8% of placebo participants (p<0.001). At 12 months, 79.5% of participants given the rVSVΔG-ZEBOV-GP vaccine had an antibody response versus 6.8% of participants in the placebo group (p<0.001). Responders during follow-up were defined as having a change in log-transformed antibody levels greater than 2 SD of the change in the placebo group at month 1.

With type 1 error = 0.0167 (2-sided) to adjust for the three comparisons, separately for adults and for children in all age groups combined, and power = 0.90, even if the percent with a positive antibody response at 12 months is 50% in a vaccine group, with equal allocation, approximately 30 participants per group (60 participants total) are needed assuming the percent in the placebo group with a positive antibody response is approximately 7%. With unequal allocation as for the rVSVΔG-ZEBOV-GP with the booster versus placebo comparison, a total of 63 participants (21 vaccinated with rVSVΔG-ZEBOV-GP with a boost and 42 vaccinated with placebo), a difference of 50% versus 7% can also be detected at 12 months with 87% power. These sample size estimates indicate that power for the planned subgroup analysis by age is also appropriate.

The planned sample size is also adequate for the comparisons with placebo if more than 4% of participants are antibody positive at baseline and excluded from the primary analysis, and if there is some missing data 12 months.

If a correlate of protection is identified, the vaccine strategies will be compared with one another at multiple time points. For the contrast with the smallest sample size (200 adults or children assigned rVSVΔG-ZEBOV-GP with a boost versus 400 vaccinated with rHAd26/MVA or rVSVΔG-ZEBOV-GP without a boost), power is 0.83 to detect an absolute difference of 15% in the antibody response (50% versus 35%) at the 0.0167 (2-sided) level of significance, assuming 10% of participants are excluded due to a positive antibody level at entry or for missing data. If the percent with a positive antibody response at 12 months is 75%, power is 0.87 to detect a 15% lower antibody response for this planned contrast.

For SAEs, we estimate that 5% of participants in the placebo group will experience an SAE by 12 months. This estimate is based on data from PREVAIL I where after 12 months of follow-up 11.8% of participants assigned to placebo developed an SAE. In PREVAIL I most of the SAEs were due to malaria events which did not require hospitalization. Thus, with the exclusion of laboratory confirmed malaria events that did not require hospitalization, the 12 month percent with SAEs in this study is expected to be lower. Among adults and children, considered separately, with type 1 error = 0.0167 (2-sided), power is 0.88 to detect an increase of 7% (to 12%) for the rHAd26/MVA and for the rVSVΔG-ZEBOV-GP without a boost strategies compared to placebo assuming 400 per group. For the rVSVΔG-ZEBOV-GP with a boost (N=200) versus placebo (N=400) comparison for adults and children, power is 0.86 to detect an increase of 9% (to 14%).

Sample size is also sufficient for comparing the vaccine strategies with the pooled placebo group for the antibody response at day 14 (an important secondary objective that address the immediacy of the immune response). For example, if the antibody response at 14 days is 25% in a vaccine group and 7% in the placebo group, fewer than 250 participants total are needed.

A sample size re-estimation will be performed before enrolment has been completed to ensure there is adequate power for both adults and children to address the primary objectives.

